5.4 Randomization Criteria

Subjects will be randomized into the study provided they have satisfied all subject selection criteria.

5.5 Lifestyle Considerations

During the entire study (screening – Visit 10) the following restrictions apply:

Subjects may be asked to remove their facial make-up at the screening visit to allow for the visual assessments to be made.

Subjects will not be permitted to use any other skin care products, including but not limited to: leave-on cosmetics, moisturizers, lotions, creams, sunscreens, soaps, cleansing, exfoliation products, etc. on their face or legs, other than the standard soap and study product(s) provided.

At all post baseline study visit days, subjects must cleanse their face and legs with the standard soap and then apply the test product (s) approximately 10-16 hrs before each study appointment (i.e. evening before).

No use of any product on the face or legs, including the standard soap and test product, within 10 hours of all instrumental measurements on visit days (no showering/bathing permitted with soaps/shampoo within this period) will be permitted.

Protocol Number: 209638 Draft Clinical Protocol

Subjects will be permitted to wash their face and legs with water only on the day of site visit. However, on the day of site visit, subjects should not wash their face or legs less than 2 hours before the first instrumental measurement is taken.

On site visit days for visits 2 and 4, the morning product application will be performed at the site after all assessments have been completed. The second application on each of the days will be performed by the subjects at home approximately 8-12 hours following the on-site application.

There should be no introduction of new products during the study including but not limited to soap, laundry detergent, or fabric softener.

Subjects should avoid wearing tight or restrictive clothing on, or around the face or over the legs.

Chemical or physical hair removal methods or bleaching or dying of the hair on the face and legs is not permitted during the study. To avoid confounding effects, subjects will be instructed to shave their legs on the first day of the washout phase and will not be permitted to shave their legs (or use any other hair removal process) at any other point during the study period until they exit the study. Subjects may use the soap provided to create a lather to shave their legs on the first day of the washout period.

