4.3 Justification for Dose

The application quantity of the study products has been selected to reflect typical consumer usage of these types of products at approximately 2 mg/cm² (Simion *et al*, 2006). The first administration will be supervised by a trained technician when the subjects are at the study site.

An 8-hour minimum period between study product applications is required, except for Day 1, where measurements of TEWL and moisturization will be further taken at 24-hours following the first supervised application. Study product will be applied following completion of all assessments and measurements.

For the home-use period, after cleansing with the supplied standard soap, subjects will be instructed to apply 2 pumps of their assigned moisturizing cream to the allocated side of their face, including forehead and chin, twice-daily (in the morning and evening). Two pumps of moisturizing cream over the surface area of a typical half-face equates to approximately 0.6 mL or 2 mg/cm². In addition, after cleansing with the standard soap, subjects will be instructed to apply a further 6 pumps of their assigned moisturizing cream to the outside of the allocated lower leg, from the bottom of the knee to above the ankle, twice-daily (in the morning and evening). 6 pumps of moisturizing cream over the surface area of the outer side of a typical lower leg equates to approximately 1.8 mL or 2 mg/cm². This will be the same application quantities for the side of the face and leg when performed at the study site, but subjects will not use the soap cleanser when at the study site.

Subjects will be reminded that, as with all skin care products when topically applied to the face, care should be taken to avoid getting the products into the eyes. If contact does occur, then subjects will be instructed to rinse the eyes thoroughly with water.

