6.1 Investigational/Study Product Supplies

The following study products will be supplied by the Clinical Supplies Department, GSK CH:

Table 6-1 Investigational/Study Product Supplies

	Test Product 1	Test Product 2	Standard Cleanser Soap	
Product Name	Developmental Moisturizing Cream 1	Developmental Moisturizing Cream 2	Simple Pure Soap	
Pack Design	40ml Bottle with piston po	125g bar soap		
Dispensing Details	A kit will be dispensed to 5 bottles	each subject containing	2 bars of soap with a soap holder	

Protocol Number: 209638 Draft Clinical Protocol

Product Master Formulation Code (MFC)	CCI	UK market place product		
	FACE: Apply 2 pumps of test product (approximately 0.3 ml × 2 = 0.6 ml) to the randomly assigned side of the face, including forehead and chin, twice-daily (in the morning and evening) after cleansing.			
	LEG: Apply 6 pumps of test product (approximately 0.3 ml × 6 = 1.8 ml) to the randomly assigned lower leg (below the knee; above the ankle) twice-daily (in the morning and evening) after cleansing.	Wet soap with warm water and work into a lather.		
Usage Instructions	Avoid contact with eyes. If contact occurs, rinse thoroughly with water.	Cleanse the entire face and both lower legs (between the knees		
	An 8-hour minimum period between daily study product applications is required, except for Day 1, where measurements of TEWL and moisturization will be further taken at 24-hours following the first supervised single application.	and the ankles). Avoid contact with eyes. If contact occurs, rinse thoroughly with water.		
	On evening prior to study visit, apply the test product approximately 10-16 hrs before each study appointment.			
	Study product will be applied following completion of all assessments and measurements under site supervision at the study site, and then 8 hours later by subject at home.			
Route of Administration	Topical dermal application			
Return Requirements	All used/unused samples to be returned.	Used soap to be retained by the subjects.		

Table 6-2 Sundry Items

Sundry Items to be supplied:

	Supplied Basis Dispensing		Diamonoina	Return/Disposal	Details
Item	Supplied By	Pack Design	Details	Used Samples	Unused Samples
Soap dish	GSK CH	Commercial Pack	1 labelled soap dish will be dispensed to contain the soap during the study.	Destroy at site using site disposal procedures	Return

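### Section 5.5 directs a home dose on the evening of Day 1, against section 4.1 and the Visit 3 rule in section 6.2, and so 11-17 h before the 24-hour single-application Corneometer reading

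*Protocol*

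**What the plan says.** Instructions that lead to a home dose on Day 1:

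- Protocol section 5.5: "On site visit days for visits 2 and 4, the morning product application will be performed at the site", followed by "The second application on each of the days will be performed by the subjects at home approximately 8-12 hours following the on-site application". The Schedule of Activities gives Visit 2 as Day 1.
- Section 5.5, for all post-baseline visit days: subjects wash with the soap, "then apply the test product (s) approximately 10-16 hrs before each study appointment (i.e. evening before". Visit 3 (Day 2) is the first post-baseline visit.
- Table 6-1 in section 6.1: "On evening prior to study visit, apply the test product approximately 10-16 hrs before each study appointment". It also describes an on-site application "and then 8 hours later by subject at home", with no visit excepted.
- Section 6.2, in its later part, repeats the 10-16 h instruction for each post-baseline visit.

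Instructions that forbid it:

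- Sections 4.1 and 6.2 both say that subjects return at 24 h (± 1 h) having used neither soap nor study product at home since the first supervised application. Both place the second application on site at Visit 3, after the Corneometer measurements.

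Rules that bear on the conflict:

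- Section 4.3: "An 8-hour minimum period between study product applications is required, except for Day 1". Table 6-1 words the exception similarly: "except for Day 1, where measurements of TEWL and moisturization will be further taken at 24-hours following the first supervised single application".
- Section 5.5 bars any product "within 10 hours of all instrumental measurements on visit days".

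**The concern.** A subject cannot follow both sets of instructions. One secondary objective is the effect of a single application on skin moisturization, measured at 30 minutes, 6 hours and 24 hours. If product is used again on the evening of Day 1, the 24-hour value reflects two applications. The extra dose goes on the treated side only, so it could enlarge the product-versus-soap difference at that time point.

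The wording also matters for conduct. Inclusion criterion 3 requires willingness to comply with the Lifestyle Considerations of section 5.5, and section 8.1.6 has subjects instructed in them. Site staff asked about the Day 1 evening dose would find opposite answers in different parts of the protocol.

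**Working it through.** This is clock arithmetic, with the first supervised application at 0 h.

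Inputs:

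- Visit 3 reading at 24 ± 1 h, i.e. 23 to 25 h (sections 4.1 and 6.2).
- Home dose 8 to 12 h after the on-site application (section 5.5).
- Product 10 to 16 h before the appointment (sections 5.5, 6.1 and 6.2).
- No product within 10 h of a measurement (section 5.5).

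**Step 1: intended design.** No home dose is taken, so the reading falls 23-25 h after the only application.

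**Step 2: the quoted sentence alone.** Gap from second dose to reading = reading time minus dose time.

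- Shortest: 23 − 12 = 11 h.
- Longest: 25 − 8 = 17 h.
- At exactly 24 h: 24 − 12 = 12 h to 24 − 8 = 16 h.

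**Step 3: both clauses of section 5.5 together.** The evening-before clause limits the gap to 10-16 h. Its overlap with 11-17 h is 11-16 h.

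**Step 4: does the 10-hour product-free rule catch this?** No. The shortest gap in steps 2 and 3 is 11 h, which satisfies the rule.

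**Step 5: are the earlier readings affected?** The earliest home dose is 8 h after the first application under the quoted sentence, or 23 − 16 = 7 h under the evening-before clause. Both come after the 6-hour reading, so the 30-minute and 6-hour readings stay clean.

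**Step 6: does the Day 1 exception resolve it?** In section 4.3 and Table 6-1 the exception is attached to the 8-hour minimum interval between applications. It shows that Day 1 was meant to be different. It does not say that the home dose is cancelled.

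**Step 7: how much of the analysis is exposed?** Count test-product-versus-soap comparisons over SAP secondary variables 1 to 8 (time points × sites × 2 products):

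- Variable 1: 1 × 1 × 2 = 2
- Variable 2: 1 × 2 × 2 = 4
- Variable 3: 3 × 2 × 2 = 12
- Variable 4: 2 × 2 × 2 = 8
- Variable 5: 5 × 2 × 2 = 20
- Variable 6: 5 × 2 × 2 = 20
- Variable 7: 3 × 2 × 2 = 12
- Variable 8: 1 × 2 × 2 = 4

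Total = 82. The 24-hour time point supplies 1 × 2 × 2 = 4. That is 4 of the 12 single-application comparisons and 4/82 = 4.9% of all secondary comparisons.

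**The case against.** The best defence is that the intent is plain. The ban between Visits 2 and 3 is specific, is stated twice and says where the second application happens, so it should prevail over a general lifestyle paragraph. The section 5.5 sentence does not even fit Visit 2: it places the application after all assessments, whereas at Visit 2 the 30-minute and 6-hour readings follow it, and the second footnote on supervised application in the Schedule of Activities excepts Visit 2 for that reason. Sections 4.1 and 6.2 pair Visit 3 with Visit 4 for the later on-site applications. All this points to a one-digit slip. The diary is also reviewed at Visit 3, when continued eligibility is checked, and sections 6.7 and 8.2 make additional applications deviations.

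The argument about intent stands, and it is why the consequence is rated minor. It does not remove the conflict. Nothing says which section prevails, and section 6.2 contains both the ban and the unexempted evening-before instruction. Diary review can find a Day 1 evening dose, but whether that dose counts as additional or as expected depends on the section staff apply. Section 12.2.2 would allow such readings to be excluded at blind data review, but no stated rule requires it, and secondary analyses use the MITT population only.

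A reader might infer three stronger things:

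- *A gap of 10-17 h for a subject following section 5.5.* That range is the union of two clauses. A 10 h gap breaks the 8-12 h clause and a 17 h gap breaks the 10-16 h clause.
- *A widespread dosing error, because the evening-before product rule is also at odds with the soap-only regression period (Visits 6-10).* Product is returned at Visit 5, so there the conflict is one of wording.
- *A lost single-application objective or a damaged primary result.* Two of the three single-application time points are untouched, and this route does not reach Day 29 facial TEWL.

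**Conclusion.** The inconsistency is certain on the text, and section 5.5 is wrong as written. A subject who follows its quoted sentence has the 24-hour Corneometer reading 11-17 h after a second dose (11-16 h if both section 5.5 clauses are met), and that reading does not measure a single application.

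The consequence is minor: one secondary time point, in analyses whose inferences SAP section 4.5 describes as exploratory. The primary endpoint, success criterion, power, and 30-minute and 6-hour readings are unaffected.

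The timing treats the stated approximate intervals as exact and takes the appointment and the reading as the same moment. The documents give neither the number of subjects who would dose that evening nor the resulting shift in Corneometer units. The subject-facing diary and instructions are not included, so whether this wording reaches subjects is unknown. Confidence is high in the conflict but not in any particular effect on the results.

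**What to change.** - **Section 5.5:** replace Visits 2 and 4 with Visits 3 and 4 in the on-site application sentence. Add that no soap or product is used at home after the Day 1 supervised application until after the Visit 3 reading.
- **Section 5.5, Table 6-1 and section 6.2:** limit the evening-before product instruction to Visits 4 and 5. Stating soap only before Visits 6-10 at the same time is an editorial tidy-up.
- **Table 6-1:** exempt Day 1 from the home dose that follows an on-site application.
- **Conduct:** treat any Day 1 evening dose as an additional use and a deviation through the existing diary process. A sensitivity analysis of the 24-hour endpoint without those records is optional.

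The cost is wording in three places. No visits, data or required analyses are added.

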5.5.1 Alcohol and Caffeine

Subjects will abstain from alcohol on study visit days until all instrumental measurements have been taken.

Subjects will abstain from consuming caffeine-containing products on study visit days until all instrumental measurements have been taken.

5.5.2 Activity

Subjects will abstain from strenuous exercise, with heavy sweating (e.g. heavy lifting, weight training, calisthenics, aerobics) at least for 24 hours prior to study site visits.

5.6 Screen Failures

Screen failures are defined as subjects who consent to participate in the clinical study but are not subsequently randomized. To ensure transparent reporting of screen failure subjects, a minimal set of screen failure information will include demography, screen failure details (e.g. withdrawal of consent), eligibility criteria, and any adverse events or incidents as applicable.

Individuals who do not meet the criteria for participation in this study (screen failure) may not be re-screened.

5.7 Sponsor's Qualified Medical Personnel

Contact information for the sponsor's appropriately qualified personnel for the study is documented in the Study Contact List located in the investigator study master file held at the study site.

The contact number is only to be used by investigational staff seeking advice on medical/dental questions or problems in the event that the established communication pathways between the investigational site and the study team are not available.

The contact number is not intended for direct use by study subjects. To facilitate access to appropriately qualified medical personnel on study-related medical questions or problems,

Protocol Number: 209638 Draft Clinical Protocol

subjects will be provided with a contact card. The contact card will provide, as a minimum, protocol identifiers, the subject's study identification number, contact information for the investigational site, and contact details in the event that the investigational site cannot be reached to provide advice on a medical question or problem identified by a healthcare professional other than the investigator.

5.8 Rater/Clinical Assessor Qualifications

All clinical assessments will be made by a single suitable trained examiner for all subjects throughout the study. The assessor will visually assess subjects for inclusion into the study at screening visit (Visit 1) and continued eligibility at the baseline visit (Visit 2).

Appendix 1 - Assessment of Overall Dryness will be used for examiner visual grading and subject self-assessment of the feeling of tightness for each side of the face and each of the legs, with half-point scores used as necessary to better describe the clinical condition. There should be no greater than 0.5-unit difference in scores between each side of the face and no greater than 1-unit different for each leg at the screening visit and at the baseline visit assessments to ensure a balance in the skin across the test sites at the visits. The examiner should be trained in the correct use of the assessment scale.

Any observed cutaneous response that can be described by the assessment of overall dryness scale will not typically be considered an adverse event. Only in the case of unusual reactions, in the opinion of the qualified dermatologist, will these reactions and the consequences observed upon evaluation be documented as AE's.

6 INVESTIGATIONAL/STUDY PRODUCTS

For the purposes of this study, per International Conference on Harmonization (ICH) guidelines, and GSK policy, investigational product is defined as a pharmaceutical form of an active ingredient, a non-medicinal product (marketed or investigational), or a placebo, being tested or used as a reference (positive or negative control), in a clinical trial. This includes a product with a marketing authorization when used or assembled (formulated or packaged) in a way different from the approved form, or when used for an unapproved indication, or when used to gain further information about an approved use.

6.1 Investigational/Study Product Supplies

The following study products will be supplied by the Clinical Supplies Department, GSK CH:

Table 6-1 Investigational/Study Product Supplies

	Test Product 1	Test Product 2	Standard Cleanser Soap	
Product Name	Developmental Moisturizing Cream 1	Developmental Moisturizing Cream 2	Simple Pure Soap	
Pack Design	40ml Bottle with piston po	125g bar soap		
Dispensing Details	A kit will be dispensed to 5 bottles	each subject containing	2 bars of soap with a soap holder	

Protocol Number: 209638 Draft Clinical Protocol

Product Master Formulation Code (MFC)	CCI	UK market place product		
	FACE: Apply 2 pumps of test product (approximately 0.3 ml × 2 = 0.6 ml) to the randomly assigned side of the face, including forehead and chin, twice-daily (in the morning and evening) after cleansing.			
	LEG: Apply 6 pumps of test product (approximately 0.3 ml × 6 = 1.8 ml) to the randomly assigned lower leg (below the knee; above the ankle) twice-daily (in the morning and evening) after cleansing.	Wet soap with warm water and work into a lather.		
Usage Instructions	Avoid contact with eyes. If contact occurs, rinse thoroughly with water.	Cleanse the entire face and both lower legs (between the knees		
	An 8-hour minimum period between daily study product applications is required, except for Day 1, where measurements of TEWL and moisturization will be further taken at 24-hours following the first supervised single application.	and the ankles). Avoid contact with eyes. If contact occurs, rinse thoroughly with water.		
	On evening prior to study visit, apply the test product approximately 10-16 hrs before each study appointment.			
	Study product will be applied following completion of all assessments and measurements under site supervision at the study site, and then 8 hours later by subject at home.			
Route of Administration	Topical dermal application			
Return Requirements	All used/unused samples to be returned.	Used soap to be retained by the subjects.		

Table 6-2 Sundry Items

Sundry Items to be supplied:

	Supplied Basis Dispensing		Diamonoina	Return/Disposal	Details
Item	Supplied By	Pack Design	Details	Used Samples	Unused Samples
Soap dish	GSK CH	Commercial Pack	1 labelled soap dish will be dispensed to contain the soap during the study.	Destroy at site using site disposal procedures	Return
BiC [®] Twin Lady Sensitive Razors	GSK CH	Commercial Pack containing 5 razors	1 razor will be supplied per subject to shave their legs on the first day of the washout phase. Subjects will not be permitted to shave	Retained by the subjects	Return

Protocol Number: 209638 Draft Clinical Protocol

their legs or use any other hair	
removal process at	
any other point	
during the study	
period until they	
exit the study.	

Supplies provided by the clinical investigational site must be stored in compliance with the label requirements in a secure place with limited or controlled access.

Detailed instructions for the return of study product/study supplies for the accountability checks and subsequent destruction which will be provided by GSK CH during the study in time for study close out visit.

6.1.1 Dosage Form and Packaging

Both the developmental test moisturizers will be supplied to the clinical site as packaged labelled bottles in kits for dispensing by site staff.

The content of the product labels will be in accordance with all applicable regulatory requirements and will be the responsibility of the GSK CH Global Clinical Supplies group. Each study label will contain, but not be limited to, protocol number, container number, directions for use and storage requirements.

Care should be taken with the supplied products and their labels so that they are maintained in good condition. It is important that all labels remain intact and legible for the duration of the study. Subjects should be instructed to not remove or deface any part of the study label.

All products supplied are for use only in this clinical study and should not be used for any other purpose.

6.1.2 Preparation and Dispensing

Both the developmental test moisturizers will be dispensed by qualified unblinded site personnel according to the randomization schedule. These staff members will not be involved in any efficacy assessments or safety aspects of the study that could be influenced by the knowledge of product a subject has been assigned to. An additional member of site staff, should ensure the dispensing procedures are completed accurately.

Subjects will be assigned to products in accordance with the randomization schedule generated by an approved GSK CH vendor, prior to the start of the study, using validated software.

6.2 Administration

Subjects will be instructed to self-administer their assigned product per the usage instructions provided.

The application quantity of each product has been selected to reflect typical consumer usage of these types of product; approximately 2 mg/cm² (Simion *et al*, 2006).

The first application of the assigned test moisturizer will be under supervision at the study site at baseline (Day 1/Visit 2), following all baseline assessments. This will be application of the test moisturizer product only; no cleansing (soap use) will be performed. Instrumental measurements of skin moisturization (using a Corneometer) will be performed at 30 minutes and 6 hours after first single product application.

Protocol Number: 209638 Draft Clinical Protocol

Subjects will return to the site on Day 2 (Visit 3), 24 hours (±1hr) after first single product application, without applying any products (no cleansing/standard soap use or study product application) at home since the first supervised use. Subjects will be permitted to wash their face with tap water only, up to 2 hours prior to measurements. Instrumental measurements of skin moisturization (using a Corneometer) will be performed at 24 hours (±1hr) after first single product application.

Second application of study product (moisturizer only) will be performed under site supervision following completion of the Corneometer measurements at Day 2 (Visit 3).

The standard soap will be used to cleanse the entire face and both lower legs (between the knees and the ankles) as needed. Subjects will be instructed to continue to apply their study product (moisturizer) to the randomly designated side of the face and the lower leg, twice-daily (in the morning and evening, approximately 8-12 hours apart), for 4 weeks (28±2 days). An 8-hour minimum period between daily study product applications is required, except for Day 1,

There will be no standard soap use or study product application in the morning of each of the assessment study site visits (i.e. visits 3, 4, and 5) of the treatment phase. Study product application (moisturizer only) will be performed under site supervision following Corneometer assessments at Day 2 (Visit 3), and TEWL and Corneometer assessments at Day 15 (Visit 4).

There will be no product application at Day 29 (Visit 5). Last application will be by the subjects at home on the evening of Day 28±2 days. The assigned test moisturizer will be returned at Day 29 (Visit 5). Subjects do not return the standard soap. The soap dish with any unused (unopened) soap and the Diary Card are returned on Day 34 (Visit 10).

Subjects will be reminded to bring all their study products (test moisturizer) and their diary cards with them to each post-baseline visit, having applied study product (s) 10-16 hrs (evening) prior to their appointment time.

Subjects will not be permitted to cleanse face or legs with anything other than water (up to 2 hours prior to the visit time) on the day of each site visit, until after all site assessments have been performed

A 6-day Regression Period where subjects will not use any product, except the standard soap, will begin on Day 29. Subjects will continue to use the standard soap to cleanse their face and legs. There will be no other product application to these areas during the regression period.

Subjects will be reminded that as with all facial skin care products, care should be taken to avoid getting into the eyes. If contact does occur, then rinse thoroughly with water.

